#### LABORATORY VALUES

Laboratory results will be summarized using Système International (SI) units, as appropriate. For all quantitative parameters listed in Section 9.7.1.8, the actual value and the change from baseline to each postbaseline visit and to the end of treatment (defined as the last on-treatment value) will be summarized by visit and by age group using descriptive statistics. Qualitative parameters listed in Section 9.7.1.8 will be summarized using frequencies (number and percentage of subjects), and changes from baseline to each postbaseline visit and to end of treatment will be reported using shift tables. Percentages will be based on the number of subjects with both nonmissing baseline and relevant postbaseline results.

Laboratory test results will be assigned a low/normal/high (LNH) classification according to whether the value was below (L), within (N), or above (H) the laboratory parameter's reference range. Within-treatment comparisons for each laboratory parameter will be based on 3-by-3 tables (shift tables) that compare the baseline LNH classification to the LNH classification at each postbaseline visit and at the end of treatment. Similar shift tables will also compare the baseline LNH classification for the highest and lowest value during the treatment period.

Appendix 1 (Sponsor's Grading for Laboratory Values) presents the criteria that will be used to identify subjects with treatment-emergent markedly abnormal laboratory values (TEMAVs). Except for phosphate, a TEMAV is defined as a postbaseline value with an increase from baseline to a grade of 2 or higher. For phosphate, a TEMAV was defined as a postbaseline value with an increase from baseline to a grade of 3 or higher. When displaying the incidence of TEMAVs, each subject may be counted once in the laboratory parameter high and in the laboratory parameter low categories, as applicable.

#### VITAL SIGNS

Descriptive statistics for vital signs parameters (ie, systolic and diastolic BP [mmHg], pulse [beats per minute], respiratory rate [per minute], body temperature [in centigrade]), and growth

parameters including measurement of height, weight (kg) changes from baseline, head circumference) will be presented by visit and by age group.

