#### Safety Analyses

Evaluation of safety will be performed on the Safety Analysis Set. Assessments that will be evaluated include AEs, SAEs, clinical laboratory results, vital signs, and 12-lead ECGs. Treatment-emergent AEs will be summarized by presenting the incidence of TEAEs and the overall incidence by age group and EIAED and non-EIAED groups. The incidence of out-of-normal-range laboratory safety tests variables will be summarized along with change from baseline in laboratory safety test variables and vital sign measurements. Descriptive summary statistics of the laboratory, vital signs, and ECG parameters will also be evaluated.

Descriptive summary statistics of changes from baseline in growth (ie, height/length, head circumference, weight) will be evaluated. These data may also be compared with normative scores to assess clinical relevance.

Changes from baseline for thyroid function and IGF-1 testing will be summarized.

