#### ELECTROCARDIOGRAMS

Descriptive statistics for ECG parameters and changes from baseline will be presented by visit and by age group.

Shift tables will present changes from baseline in ECG interpretation (categorized as normal; abnormal, not clinically significant; and abnormal, clinically significant) to end of treatment.

In addition, the number (percentage) of subjects with at least 1 postbaseline abnormal ECG result in QTcF during the treatment period will be summarized. Clinically borderline and abnormal ECG results in QTcF will be categorized as follows:

Absolute QTc interval prolongation:

- QTc interval 430-450 msec
- QTc interval >450 msec
- QTc interval >500 msec

Change from baseline in QTc interval:

- QTC interval increases from baseline 30-60 msec
- QTC interval increases from baseline >60 msec

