#### VITAL SIGNS

Vital sign values will be evaluated on an individual basis by subject. Abnormal vital sign values will be identified as those outside (above or below) the reference range, where appropriate. Reference ranges for vital sign parameters will be included in the clinical study report for this protocol. Descriptive summary statistics (eg, mean, standard deviation, median, minimum, maximum) for vital sign parameters and changes from baseline (Visit 2) to each visit and to the last visit in the Extension Phase (Follow- up Visit, Week 56) will be evaluated for each cohort and overall.

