5.3.4 Examination of Subgroups

All analyses will be provided by age cohort (1 to ≤ 6 months, > 6 to ≤ 12 months, >12 to < 24 months, and 24 to <48 months). Summaries of demography, seizure data, and TEAEs may be further presented by inducer/non-inducer subgroup. Growth parameters (height, weight, thyroid and insulin-like growth factor-1 [IGF-1] parameters) may also be summarized by sex.

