5.6.4 Vital Signs

Descriptive statistics for vital signs parameters (ie, systolic and diastolic BP [mmHg], pulse [beats per minute], respiratory rate [per minute], body temperature [in centigrade]) will be presented by visit and by age group.

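### SAP 5.6.4 omits the vital-sign change from baseline that the protocol synopsis plans, leaving raw means whose rows after Week 12 hold different children

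*Protocol*

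**What the plan says.** Vital signs are a secondary safety endpoint, and the documents describe their summary in four ways.

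- Protocol synopsis, Safety Analyses: the plan includes "change from baseline in laboratory safety test variables and vital sign measurements".
- Protocol 9.7.1.8, Vital Signs (core study): vital signs and growth share one sentence, which ends "parameters including measurement of height, weight (kg) changes from baseline, head circumference) will be presented by visit and by age group". The phrase about baseline sits inside the list, after weight, and the parentheses do not balance.
- SAP 5.6.4: blood pressure, pulse, respiratory rate and temperature are listed, ending "body temperature [in centigrade]) will be presented by visit and by age group". Neither change from baseline nor an end-of-treatment summary is named.
- Protocol Appendix 3, Vital Signs (Extension): descriptive statistics are planned "for vital sign parameters and changes from baseline (Visit 2) to each visit" and to the last visit.

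The neighbouring endpoints are handled differently. For ECG the protocol says "Descriptive statistics for ECG parameters and changes from baseline will be presented by visit and by age group", and SAP 5.6.5 agrees. For laboratory data, Protocol 9.7.1.8 and SAP 5.6.3 plan both the value and its change, at each visit and at end of treatment. SAP 8.2.1 defines a baseline for all safety endpoints. SAP Section 7 reports no major changes from the protocol.

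On grouping, SAP Section 5 sets age cohort and overall as the default. SAP 5.3.4 adds an optional split: "Summaries of demography, seizure data, and TEAEs may be further presented by inducer/non-inducer subgroup". Vital signs are not in that list. SAP 8.2.2 maps visits to study weeks with separate window tables for EIAED and non-EIAED children.

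**The concern.** If the tables follow SAP 5.6.4 as written, the only vital-sign summary is a raw mean for each study week within an age cohort. A raw mean can be compared across weeks only when the same children contribute. Up to Week 12 the two schedules match, so membership changes only through dropout or missing data. After Week 12 the schedule itself changes the membership of the row.

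A reader scanning a cohort table for a trend in pulse or blood pressure could then take a change in who was measured for a change within children, or miss a real change for the same reason. The cohorts are small (minimum 6, 5 and 5 below 24 months), so a few children entering or leaving a row can move its mean visibly. Change from baseline is the usual protection, and it is what the SAP leaves out here.

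**Working it through.** The plan gives no figure to reproduce on this point. The check has two parts.

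**1. Who is in each vital-sign row.** From Protocol Tables 4 and 5 and the window tables in SAP 8.2.2:

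| Study week | Non-EIAED | EIAED | On-treatment row holds |
|---|---|---|---|
| 12 | end of Titration | Titration | both |
| 14 | Maintenance | no visit | non-EIAED only |
| 16 | end of Maintenance | end of Titration | both |
| 18 | no visit | Maintenance | EIAED only |
| 20 | off-drug follow-up, coded Week 99 | end of Maintenance | EIAED only |

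The protocol requires at least 16 subjects aged 1 to <24 months, 6 to 8 of them on an EIAED. Before dropout, the infants contributing are 16 at Week 12, 8 to 10 at Week 14, 16 at Week 16, and 6 to 8 at Weeks 18 and 20.

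Laboratory tests and ECGs are not scheduled at Week 14 or 18. Both groups have them at Weeks 12 and 16, so only their Week 20 row is single-group.

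**2. How far membership alone can move a raw mean.** Suppose no child changes, let σ be the between-child SD, and treat the n₂ children who remain as a random subset of the n₁ in the fuller row. The difference between the two row means then has

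SD = σ × √(1/n₂ − 1/n₁).

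- All 16 infants to 7 on EIAEDs (Week 16 to Week 18 or 20): √(1/7 − 1/16) = √0.0804 = 0.28σ. With 6 on EIAEDs it is √(1/6 − 1/16) = 0.32σ; with 8 it is √(1/8 − 1/16) = 0.25σ.
- Cohort of 5 with an assumed 2 on inducers, Week 16 to Week 18 or 20: √(1/2 − 1/5) = √0.30 = 0.55σ.
- Same cohort, Week 12 to Week 14 (5 children to 3): √(1/3 − 1/5) = √0.133 = 0.37σ.

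The documents give no SD for any vital sign, so the results stay in units of σ. The 16-infant figures describe the three infant cohorts together. The SAP's overall column would also contain the children aged 2 to <4 years, of whom this study may enrol 1 to 26.

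The formula gives random scatter. If the two groups also differ by a stable amount d, the raw mean relative to the non-EIAED level moves systematically. With an EIAED fraction f of 6/16 to 8/16, it runs f·d at Week 12, 0 at Week 14, f·d at Week 16, and d at Weeks 18 and 20. Change from baseline removes both effects, because a child who has not changed contributes zero to every row.

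**The case against.** The strongest case against is that this is a wording mismatch, not a missing analysis. The synopsis plans the change, the SAP defines the baseline and claims no major departure from the protocol, and the table shells (SAP Section 11) are in a separate document that may already show it. Much of that stands. It would be wrong to say that the plan as a whole has no vital-sign change from baseline. But SAP 5.6.4 is the text the tables will be built from, and its laboratory and ECG neighbours state the change explicitly, so silence there should not be left to the shells.

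Some stronger readings are tempting and are not supported:

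- *Laboratory and ECG tables suffer equally.* They do not. Both have change from baseline by visit; laboratory data have shift tables by visit and to end of treatment, and ECG interpretation has one to end of treatment. Only their Week 20 row is single-group.
- *Week 16 mixes dose stages.* The period labels differ, but Protocol Table 2 schedules no titration for EIAED children at Week 16, and children should have held their last Titration dose for at least 2 weeks before Maintenance. Both groups should be on a settled dose.
- *No summary could represent end of treatment for both groups.* Footnote b to each SAP window table defines a core-study end-of-treatment value. SAP 5.6.4 simply does not use it.

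It is also fair that the 0.55 SD figure depends on an assumed split in a minimum-size cohort, and that these are descriptive tables in an uncontrolled study.

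**Conclusion.** The point holds for vital signs. SAP 5.6.4 omits a within-child summary that the synopsis plans, and SAP Section 7 does not acknowledge it. Followed literally, it leaves raw means whose rows after Week 12 change membership by schedule. The resulting scatter is about 0.28 between-child SD for the infants together (0.25 to 0.32 across the permitted 6 to 8 on EIAEDs) and about 0.55 SD in a cohort of 5. These sizes assume no within-child change, no dropout, minimum enrolment and, for the cohort figure, 2 of 5 on inducers.

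A reader might infer that week-to-week differences in these tables are artefacts of membership. The documents support less: such differences may partly reflect membership, only after Week 12, and real change is not excluded. Laboratory and ECG summaries are much less affected and do not need the same correction.

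**What to change.** In SAP 5.6.4, state that for every vital sign the value and the change from baseline will be summarised at each postbaseline visit and at end of treatment, by age cohort and overall, with n in each row. Use the baseline in SAP 8.2.1 and the end-of-treatment definition already in SAP 8.2.2. Repair the sentence in Protocol 9.7.1.8 so that change from baseline clearly covers all the listed measurements, as the synopsis intends.

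Preferably, also label or split the vital-sign rows after Week 12, either by EIAED status or by period: end of Titration (Week 12 non-EIAED, Week 16 EIAED), mid-Maintenance (14, 18) and end of Maintenance (16, 20). This is a secondary presentation choice.

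The cost is SAP wording and table programming, with no new data. Period rows would join values scheduled 4 weeks apart in study time, and split columns would hold few children: 3 and 2 in the assumed cohort of 5.

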#### ELECTROCARDIOGRAMS

Descriptive statistics for ECG parameters and changes from baseline will be presented by visit and by age group.

Shift tables will present changes from baseline in ECG interpretation (categorized as normal; abnormal, not clinically significant; and abnormal, clinically significant) to end of treatment.

In addition, the number (percentage) of subjects with at least 1 postbaseline abnormal ECG result in QTcF during the treatment period will be summarized. Clinically borderline and abnormal ECG results in QTcF will be categorized as follows:

Absolute QTc interval prolongation:

- QTc interval 430-450 msec
- QTc interval >450 msec
- QTc interval >500 msec

Change from baseline in QTc interval:

- QTC interval increases from baseline 30-60 msec
- QTC interval increases from baseline >60 msec

### OTHER SAFETY ANALYSES

### Growth

Descriptive summary statistics of changes from baseline in height, weight, and head circumference will be evaluated for each cohort and overall. This data will be compared with normative scores to assess clinical relevance.

Changes from baseline for thyroid function and IGF-1 testing will be summarized.

## 9.7.2 Determination of Sample Size

Study E2007-G000-238 will use population PK modeling to determine PK in pediatrics  $\geq 1$  to <24 months and from 2 to less than 4 years of age and compare these data to PK in adolescents and adults. In Study E2007-G000-232, data were obtained in 42 pediatric subjects  $\geq 2$  to <12 years of age, with approximate equal numbers enrolled in the age ranges of  $\geq 2$  to  $\leq 6$  and  $\geq 7$  to <12 years. (revised per Amendment 02)

Given the narrower age range planned for Study 238 compared with Study 232, and the fact that the PK data from this study will be pooled with the data from subjects  $\geq 2$  to <12 years of age, it is proposed that PK data obtained in at least 16 subjects  $\geq 1$  to <24 months of age would

be adequate to characterize the PK in this age group. The sample size will be increased to at least 24 subjects if dose-normalized (to 8 mg) exposure in the Maintenance Period from the first 16 subjects in this study is not comparable to existing data in subjects aged  $\geq 2$  to 18 years.

In order to compare the PK of pediatric subjects aged 2 to <4 years of age with the PK of pediatric subjects aged >4 years of age, a total of 26 subjects with 13 EIAED subjects and 13 non-EIAED subjects will be enrolled and pooled across clinical studies of perampanel with PK assessment. This estimate of the required sample size assumes the inter-subject variability of 46.8% (CPMS-E2007-015-v1), equivalent to a coefficient of variation (CV) on the log scale of 0.445, that provides a sufficient number of subjects to target a 95% confidence interval within 60% and 140% of the point estimate for the geometric mean clearance of perampanel (equal to 0.638 L/h; determined using population PK modeling) with at least 80% power. (revised per Amendment 02)

## 9.7.3 Interim Analysis

After every 4th subject in the age group 1 to less than 24 months completes the Maintenance Period an interim analysis (safety, tolerability, and PK) will be conducted where dosenormalized exposure will be compared to that observed in other studies in subjects between  $\geq 2$ and <18 years of age for evidence of systematic deviations potentially warranting dose adjustment in this age group or for other subjects enrolled in the study. PK data collected in older age cohort (2 to less than 4 years) will also be examined in the interim PK analyses. (revised per Amendment 02)

All data from the Pretreatment and Treatment Phases (Core Study) will be analyzed when all subjects have completed the Maintenance Period. In addition, a final analysis of data from the Pretreatment, Treatment, and Extension Phases will be analyzed when all subjects have completed the Extension Phase.

An independent Data Monitoring Committee (DMC) will be constructed to monitor the safety data. The responsibilities, membership, and purpose of the DMC, the timing of the meeting(s), and an outline of the plan for review of the safety data will be documented in the DMC Charter.

### 9.7.4 Other Statistical/Analytical Issues

Not applicable.

## 9.7.5 Procedure for Revising the Statistical Analysis Plan

If the statistician determines that the analysis plan needs to be revised after this study starts, the person in charge of the analysis plan and the study director will examine the validity of the revision and the impact of the revision against the evaluation of this study and determine if the revision should be made. The details of revision will be described in the clinical study report for this protocol.

## 11 PROCEDURES AND INSTRUCTIONS (ADMINISTRATIVE PROCEDURES)

## 11.1 Changes to the Protocol

Any change to the protocol requires a written protocol amendment or administrative change that must be approved by the sponsor before implementation. Amendments specifically affecting the safety of subjects, the scope of the investigation, or the scientific quality of the study require submission to health or regulatory authorities as well as additional approval by the applicable IRBs/IECs. These requirements should in no way prevent any immediate action from being taken by the investigator, or by the sponsor, in the interest of preserving the safety of all subjects included in the study. If the investigator determines that an immediate change to or deviation from the protocol is necessary for safety reasons to eliminate an immediate hazard to the subjects, the sponsor's medical monitor and the IRB/IEC for the site must be notified immediately. The sponsor must notify the health or regulatory authority as required per local regulations.

Protocol amendments that affect only administrative aspects of the study may not require submission to health or regulatory authority or the IRB/IEC, but the health or regulatory authority and IRB/IEC should be kept informed of such changes as required by local regulations. In these cases, the sponsor may be required to send a letter to the IRB/IEC and the Competent Authorities detailing such changes.

## **11.2** Adherence to the Protocol

The investigator will conduct the study in strict accordance with the protocol (refer to ICH E6, Section 4.5).

## **11.3 Monitoring Procedures**

The sponsor's/CRO's CRA will maintain contact with the investigator and designated staff by telephone, letter, or email between study visits. Monitoring visits to each site will be conducted by the assigned CRA as described in the monitoring plan. The investigator will allow the CRA to inspect the clinical, laboratory, and pharmacy facilities to assure compliance with GCP and local regulatory requirements. The CRFs and subject's corresponding original medical records (source documents) are to be fully available for review by the sponsor's representatives at regular intervals. These reviews verify adherence to study protocol and data accuracy in accordance with local regulations. All records at the site are subject to inspection by the local auditing agency and to IRB/IEC review.

In accordance with ICH E6, Section 1.52, source documents include, but are not limited to, the following:

• Clinic, office, or hospital charts

- Copies or transcribed health care provider notes that have been certified for accuracy after production
- Recorded data from automated instruments such as x-rays, and other imaging reports (eg, sonograms, CT scans, magnetic resonance images, radioactive images, ECGs, rhythm strips, EEGs, polysomnographs, pulmonary function tests) regardless of how these images are stored, including microfiche and photographic negatives
- Pain, quality of life, or medical history questionnaires completed by subjects
- Records of telephone contacts
- Diaries or evaluation checklists
- Drug distribution and accountability logs maintained in pharmacies or by research personnel
- Laboratory results and other laboratory test outputs (eg, urine pregnancy test result documentation and urine dip-sticks)
- Correspondence regarding a study subject's treatment between physicians or memoranda sent to the IRBs/IECs
- CRF components (eg, questionnaires) that are completed directly by subjects and serve as their own source

## 11.4 Recording of Data

A CRF is required and must be completed for each subject by qualified and authorized personnel. All data on the CRF must reflect the corresponding source document, except when a section of the CRF itself is used as the source document. Any correction to entries made on the CRF must be documented in a valid audit trail where the correction is dated, the individual making the correct is identified, the reason for the change is stated, and the original data are not obscured. Only data required by the protocol for the purposes of the study should be collected.

The investigator must sign each CRF. The investigator will report the CRFs to the sponsor and retain a copy of the CRFs.

## **11.5** Identification of Source Data

All data to be recorded on the CRF must reflect the corresponding source documents.

## **11.6 Retention of Records**

The circumstances of completion or termination of the study notwithstanding, the investigator is responsible for retaining all study documents, including but not limited to the protocol, copies of CRFs, the Investigator's Brochure, and regulatory agency registration documents (eg, Form FDA 1572, ICFs, and IRB/IEC correspondence. The site should plan to retain study

documents, as directed by the sponsor, for at least 2 years after the last approval of a marketing application in an ICH region and until there are no pending or contemplated marketing applications in an ICH region or at least 3 years have elapsed since the formal discontinuation of clinical development of the investigational product.

It is requested that at the completion of the required retention period, or should the investigator retire or relocate, the investigator contact the sponsor, allowing the sponsor the option of permanently retaining the study records.

